3.5 Microarray analysis

Whole genome expression (38,000 genes) will initially be done on purified CD4+/CD8+ T-cells at baseline, week 4 and at week 24 of MVC intensification. However, considering that other immune cells, such as monocytes, also express CCR5 these cells will be stored for future microarray analyses.

3.6 Lumbar Puncture

Standard lumbar puncture-related adverse events will be monitored following all visits. Lumbar punctures will be performed under aseptic conditions at the clinical facilities of the HNRC by a neurologist, an internist, or by a trained registered nurse working under the supervision of the neurologist. Standard risks associated with HNRC medical procedures include 1) venipuncture: the risk of pain, bruising, and a very low risk infection; and 2) lumbar puncture: the risk of pain, bruising and a very low risk of infection as well as a risk of post-dural puncture cephalgia which can range from mild to severe.

Routine clinical lab assays (cell counts, glucose, total protein) will be performed on all CSF. HIV RNA will be measured with a modified version of the Biomerieux assay validated to quantify HIV as low as 2 copies/mL in CSF [51]. MVC concentrations will be measured in plasma and CSF. Remaining specimens will be aliquoted and then stored at -70C at the HIV Neurobehavioral Research Center (HNRC) Specimen Bank.

Local back pain will be minimized by injection of an anesthetic, 1% lidocaine into the subcutaneous tissue surrounding the needle puncture site. Oral analgesics and anti-inflammatory medications will be provided when necessary. Following LP, patients will be observed for 10-15 minutes. Over 3,000 LPs have been performed at the HNRC using non-cutting or "pencil point" spinal needles that reduce the risk of post-LP cephalgia. A site clinician will be available by pager 24 hours-per-day to respond to problems, should they occur. If post-LP headache occurs, initial conservative management will include recumbency, hydration, and oral analgesics. When headaches are prolonged, a blood patch, involving an epidural injection of a sample of the subject's own blood, may be performed by consulting anesthesiologists. This is extremely effective in aborting post-LP headache, but is only necessary in fewer than 1% of HNRC subjects. Palliative procedures will be performed at no cost to the participant.

Lumbar punctures will not be performed if any medical contraindication to the procedure is identified. LPs will be deferred when factors associated with increased risk of bleeding are present, such as a clinical history of bleeding diathesis, ongoing treatment with anticoagulants or platelet counts $<50,000/\text{mm}^3$. LPs also will be deferred when signs of untreated systemic or local infection are present. If a subject becomes uncomfortable, the procedure will be discontinued.

4.0 SELECTION AND ENROLLMENT OF SUBJECTS

4.1 Inclusion Criteria (Main Study)

- 4.1.1 HIV-1 infection documented by a rapid HIV test or any licensed ELISA test kit and confirmed by a different method ELISA, Western blot, rapid HIV test, or plasma HIV-1 RNA assay at any time prior to study entry. Alternatively, if a licensed ELISA is not available, two HIV-1 RNA values >2000 copies/mL at least 24 hours apart by any CLIA certified laboratory may be used to document HIV-1 infection at any time prior to study entry.
- 4.1.2 All available CD4+ T cell counts within the last 12 months of screening below 350 cells/ mm^3 (minimum of 3 values obtained ≥ 30 days apart).
- 4.1.3 CD4+ cell count below than 350 cells/ mm^3 determined by site clinical laboratory within 30 days of screening.
- 4.1.4 Subject receiving a stable (for at least 6 months) antiretroviral regimen consisting of at least 2 NRTIs and either a protease inhibitor boosted with low dose ritonavir or an NNRTI. A stable regimen is defined as no additions or deletions for more than 14 cumulative days.
- 4.1.5 Subject considered to be receiving initial HIV regimen (history of medication substitution for toxicity is allowed).
- 4.1.6 All available plasma HIV RNA levels within the last 12 months are below the level of detection. Isolated values that are detectable but < 1000 copies will be allowed as long as the plasma HIV RNA levels before and after this detectable time point are undetectable – The subject should have a minimum of 3 values obtained ≥ 30 days apart.
- 4.1.7 Screening plasma HIV RNA levels below level of detection (< 50 copies RNA/mL using Roche Amplicor or < 75 copies/mL using Bayer bDNA) obtained by site clinical laboratory within 30 days of screening.
- 4.1.8 Greater than 90% adherence to HIV therapy within the preceding 30 days, as determined by self-report.

- 4.1.9 Laboratory values obtained by screening laboratories within 30 days of entry:
- Absolute neutrophil count (ANC) $\geq 750/\text{mm}^3$.
 - Hemoglobin ≥ 8.0 g/dL.
 - Platelet count $\geq 50,000/\text{mm}^3$.
 - Calculated creatinine clearance (CrCl) ≥ 50 mL/min as estimated by the Cockcroft-Gault equation:
 - * For men, $(140 - \text{age in years}) \times (\text{body weight in kg}) \div (\text{serum creatinine in mg/dL} \times 72) = \text{CrCl (mL/min)}$
 - * For women, multiply the result by 0.85 = CrCl (mL/min)
 - AST (SGOT), ALT (SGPT), and alkaline phosphatase $\leq 5 \times \text{ULN}$.
 - Total bilirubin $\leq 2.5 \times \text{ULN}$ (unless subject receiving atazanavir).
- 4.1.8 Females of childbearing potential must have a negative serum pregnancy test at screening and agree to use a double-barrier method of contraception throughout the study period.
- 4.1.9 Karnofsky performance score ≥ 70 .
- 4.1.10 Men and women age ≥ 18 years.
- 4.1.11 Ability and willingness of subject or legal guardian/representative to give written informed consent.
- 4.2 Inclusion Criteria (CSF Sub-Study)
- 4.2.1 Enrollment in the MVC parent protocol.
- 4.2.2 Willingness to undergo lumbar puncture.
- 4.3 Exclusion Criteria (Main Study)
- 4.3.1 Current antiretroviral regimen contains tenofovir disoproxil fumarate AND didanosine in combination.
- 4.3.2 History of chronic hepatitis C (defined as HCV antibody positive and HCV RNA detectable).
- 4.3.3 History of chronic active hepatitis B (defined as surface antibody negative, surface antigen positive and HBV DNA detectable).
- 4.3.4 Concurrent use of G-CSF or GM-CSF.
- 4.3.4 Prior or concurrent use of IL-2.

- 4.3.5 Prior or concurrent use of a CCR5 inhibitor.
- 4.3.6 Active drug or alcohol use or dependence that, in the opinion of the investigator, would interfere with adherence to study requirements.
- 4.3.7 Use of any immunomodulator, HIV vaccine, or investigational therapy within 30 days of study entry.
- 4.3.8 Use of human growth hormone within 30 days prior to study entry.
- 4.3.9 Initiation of testosterone or anabolic steroids within 30 days prior to study entry. (Exception: Chronic replacement dosages in patient's with diagnosed hypogonadism is allowed).
- 4.3.10 Evidence of splenic sequestration or suppressed bone marrow function:
 - Clinical or radiographic evidence of significant splenomegaly.
 - History of leukemia or lymphoma.
 - History of myelosuppressive chemotherapy or irradiation
- 4.4 Exclusion Criteria (CSF Sub-Study)
 - 4.4.1 Relative or absolute contraindication to lumbar puncture, such as current coagulopathy, thrombocytopenia (platelets < 50,000/ μ L), hemophilia, or use of anticoagulant medication.
- 4.5 Study Enrollment Procedures

Prior to implementation of this protocol, sites must have the protocol and consent form approved by their local institutional review board (IRB). Sites must be registered with and approved by the CCTG Data Unit. Site registration must occur before any subjects can be enrolled in this study.

Once a candidate for study entry has been identified, details will be carefully discussed with the subject. The subject will be asked to read and sign the consent form that was approved by both the local IRB and the CCTG Data Center.

A patient identification number (PID) will be assigned to each patient screened for the study. PIDs will include a site code and three-digit extension. PIDs should not be reassigned even if the patient fails to enter the study. The PID must be included on every CRF and patient blood sample. Each site must maintain a master list of PIDs in a central location. The patient registration and inclusion/exclusion CRF will be entered into the online CCTG data system

4.6 Co-enrollment Guidelines

Co-enrollment in this study and other studies will be discussed with the protocol team and will be decided on a case by case basis.

5.0 STUDY TREATMENT

5.1 Dosing, Administration, and Duration

NOTE: Maraviroc will be dose-adjusted for concomitantly administered HIV medications according to the manufacture's recommendations:

5.1.1 Dosing

5.1.1.1 with strong CYP3A4 inhibitors, including:

- Protease inhibitors (except tipranavir/ ritonavir)
- Delavirdine
- ketoconazole, itraconazole, clarithromycin, nefazadone, telithromycin
- Darunavir/r + etravirine

MVC 150 mg twice daily

5.1.1.2 with non-inducers/ non-inhibitors of CYP3A4, including:

- Tipranavir/ ritonavir
- Nevirapine
- All NRTIs
- Enfuvirtide

MVC 300 mg twice daily

5.1.1.3 with strong CYP3A4 inducers, including:

- Efavirenz, etravirine
- rifampin

MVC 600 mg twice daily

5.1.4 Administration

NOTE: Maraviroc should be co-administered at the same time as the subject's other HIV medications. All other HIV medications should be administered according to each medication's recommended dosing.

5.1.4.1 MVC will be administered as a single 150 or 300 mg tablet or two 300 mg tablets PO twice daily with or without food

5.1.3 Duration

5.1.3.1 Maraviroc Therapy Intensification: Each subject will receive 24 weeks of therapy.

5.1.3.2 Post-Therapy Intensification: After 24 weeks, MVC will be discontinued and each subject will continue on baseline background HIV regimen, without Maraviroc, for an additional 12 weeks.

5.2 Product Formulation and Preparation

5.2.1 Maraviroc (Selzentry™, MVC): 150 or 300 mg tablets. Store at room temperature; 15° - 30° C (59° – 86° F).

5.3 Product Supply, Distribution, and Pharmacy

5.3.1 Study Product Acquisition

Study medications will be provided by Pfizer. All other HIV medications will not be supplied by the study, but will be made available to patients via prescription at cost to the patient and/or patient's health insurance.

5.3.2 Investigational Agent Accountability

The clinical site pharmacist is required to maintain complete records of all study products received from this study. All unused study products must be returned to the sponsors after the study is completed or terminated.

5.4 Concomitant Medications

5.4.1 Required Medications

5.4.1.1 Study medications (Maraviroc)

5.4.2 Prohibited Medications

NOTE: This list applies only to MVC. Refer to manufacture's recommendations for potential drug interactions/ contraindications for background HIV medications.

- 5.4.2.1 All investigational drugs and HIV vaccines
- 5.4.2.2 The combination of efavirenz + rifampin
- 5.4.2.3 Any immunomodulators
- 5.4.2.4 Systemic cytotoxic chemotherapy
- 5.4.2.5 All herbal products, including St John's wort, should be avoided because of the unknown drug interactions between herbal products and the antiretroviral drugs used in this study.

5.4.3 Precautionary Medications

NOTE: Refer to the individual package inserts for additional information regarding potential drug interactions that may require therapeutic drug monitoring and/or adjustment of concomitant medications. Competition for primary CYP3A metabolism or other mechanisms by study drugs could result in inhibition or stimulation of the metabolism of these drugs and create the potential for serious and/or life-threatening reactions such as cardiac arrhythmias, prolonged or increased sedation, and respiratory depression.

- 5.4.3.1 Systemic medications that interact at CYP3A as substrates, inhibitors, or inducers of the enzyme must be used with caution. These include but are not limited to:

Agent by Class	Precautionary Concomitant Medications
Alternative/complementary	Milk Thistle
Analgesics	Opioids, including: Codeine Methadone Meperidine Morphine Pentazocine (Talwin™)
Anesthetics	Propofol (Diprivan™)
Anti-arrhythmics	Amiodarone (Cordarone®) Bepridil (Vasacor®) Disopyramide (Norpace™) Encainide (Enkaid™)

Agent by Class	Precautionary Concomitant Medications
	Lidocaine (Xylocaine™)
	Mexiletine (Mexitil™)
	Quinidine (Quinidex®)
Anti-convulsants	Carbamazepine (Tegretol™)
	Lamotrigine (Lamictal™)
	Phenobarbital (Luminal™)
	Phenytoin (Dilantin™)
	Valproic acid (Depakene™)
Anti-histamines	Chlorpheniramine (Chlor-Trimetron™ and others)
	Diphenhydramine (Benadryl™ and others)
Anti-infectives	Acyclovir (Zovirax™)
	Aminoglycosides
	Amphotericin B (Amphocin™, Fungizone™)
	Cidofovir (Vistide™)
	Clarithromycin (Biaxin™)
	Dapsone
	Erythromycin (E-mycin™ and others)
	Fluconazole (Diflucan™)
	Ganciclovir (Cytovene™)
	Isoniazid
	Systemic Itraconazole (Sporonox®)
	Systemic Ketoconazole (Nizoral®)
	Ribavirin (Virazole™)
	Rifabutin (Mycobutin®)
	Vancomycin (Vancocin™, Vancoled™)
	Voriconazole (Vfend)
Beta blockers (selected agents listed, caution should be exercised for the entire class)	Atenolol (Tenormin™)
	Metoprolol (Lopressor™, Toprol™)
	Propranolol (Inderal™, Inderide™,

Agent by Class	Precautionary Concomitant Medications
	and others)
Calcium channel blockers (selected agents listed, caution should be exercised for the entire class)	Amlodipine (Norvasc®)
	Diltiazem (Cardizem® and others)
	Felodipine (Plendil®)
	Isradipine (DynaCirc®)
	Lacidipine (Lacipil™)
	Nicardipine (Cardene®)
	Nifedipine (Adalat™ and Procardia®)
	Nimodipine (Nimotop®)
	Nisoldipine (Sular®)
	Nitrendipine (Nitrendipine™)
	Verapamil (Calan™ and Isoptin®)
Hormonal agents	Estrogens and Progesterones
	Glucocorticoids
Hypoglycemics	Pioglitazone (Actos™)
HMG Co Reductase Inhibitors	Atorvastatin (Lipitor®)
	Fluvastatin (Lescol®)
Psychiatric medications	Bupropion (Wellbutrin®, Zyban®)
	Chlorpromazine (Thorazine™)
	Clozapine (Clozaril®)
	Fluoxetine (Prozac™ and others)
	Nefazodone (Serzone®)
	Paroxetine (Paxil™)
	Risperidone (Risperdal®)
	Venlafexine (Effexor®)
Tricyclic Antidepressants (including but not limited to)	Amitriptyline (Elavil™ and others)
	Desipramine (Norpramin™ and others)
	Imipramine (Tofranil™ and others)
	Nortriptyline (Pamelor™ and others)

Agent by Class	Precautionary Concomitant Medications	
Sedative/Hypnotics	All benzodiazepines	
	Alprazolam (Xanax™)	
	Clorazepate (Tranxene™)	
	Diazepam (Valium™)	
	Estazolam (ProSom™)	
	Flurazepam (Dalmane™)	
	Oxazepam (Serax™)	
	Temazepam (Restoril™)	
	Busprione (Buspar™)	
	Zaleplon (Sonata™)	
	Zolpidem (Ambien™)	
	Other agents	Chlorzoxazone (Parafon Forte™)
Cimetidine (Tagamet™)		
Naloxone (Narcan™)		
Piroxicam		
Promethazine (Mepergan™, Phenergan™)		
Sildenafil (Viagra®)		
Warfarin (Coumadin™)		

NOTE: For additional information and information updates please refer to:

http://www.hivdruginteractions.org/new/Uploaded_Attachment/52_Maraviroc%20Oct07.pdf

5.5 Adherence Assessment

Throughout the study, the documentation of adherence to study drugs and concomitant HIV medications is essential. During each visit an evaluation of adherence to study medications will be done by study personal and the clinical importance of strict adherence will be reinforced with subjects. An evaluation of study medication adherence will be done during each study visit at weeks 2, 4, 8, 12, 24 and 36.

6.0 CLINICAL AND LABORATORY EVALUATIONS

CCTG 590
Protocol version 1.0
August 13, 2008

6.1 Schedule of Events – Clinical Evaluations

	Screening	Pre-Entry	Entry	Maraviroc Therapy Intensification (24 weeks)					Post-Maraviroc Intensificatoin	Treatment Failure, Tox or Premature D/C
	Within 30 days of entry	> 48 hrs before entry	Day 0	Week 2	Week 4	Week 8	Week 12	Week 24	Week 36	
Informed Consent	X									
Medical/Medication History	X									
Documentation of HIV	X									
Clinical Assessment / AE			X	X	X	X	X	X	X	X
Documentation of within criteria HIV RNA and CD4 prior to screen labs	X									
Complete Physical Exam			X							X
Targeted Physical Exam							X	X	X	
Start and Dispense Drug			X		X		X			
Stop and Collect Drug								X		X
Concomitant Medications	X		X	X	X	X	X	X	X	X
Adherence Assessment	X		X	X	X	X	X	X	X	X

CCTG 590
Protocol version 1.0
August 13, 2008

Schedule of Events – Laboratory Evaluations

	Screening	Pre-Entry	Entry	Maraviroc Therapy Intensification (24 weeks)					Post-Maraviroc Intensification	Treatment Failure, Tox or Premature D/C
	Within 30 days of entry	> 48 hrs before entry	Day 0	Week 2 (± 1 wk)	Week 4 (± 1 wk)	Week 8 (± 2 wk)	Week 12 (± 2 wk)	Week 24 (± 2 wk)	Week 36 (± 2 wk)	
Hematology (local lab)	X		X	X	X	X	X	X	X	X
Prothrombin time (local lab) †	X									
Chemistry / LFT (local lab)	X				X		X	X	X	X
Pregnancy test (local lab)	X	And anytime when suspected								
CD4+/CD8+ (local lab)	X		X	X	X	X	X	X	X	X
§ CD4 ≤ 350; HIV RNA ≤ 50	X									
Plasma HIV-1 RNA PCR (local lab)	X		X		X			X	X	X
Plasma for MVC levels †			X		X			X		
Extended flow cytometry & PBMC collection (UCSD lab)		X	X		X			X		
Microarray - PBMCs collection (local processing in real-time)			X		X			X		
Lumbar puncture†			X		X			X		
Plasma for storage			X		X			X	X	
Serum for storage			X		X			X	X	
Ship ambient sample for extended flow in real-time		X	X		X			X		
Ship frozen all stored PBMCs, plasma and serum									X	
HIV Resistance & Tropism testing										X

§ If available within 30 days of screen then do not need to repeat laboratory test and can use value obtained within 90 days as screen value

† Only for subjects co-enrolled in the central nervous system sub-study

6.2 Definitions for Schedule of Events – Timing of Evaluations

6.2.1 Evaluations Prior to Study Entry

Occur prior to the subject taking any study medications, treatments, or interventions.

Patient Registration

A patient identification number (PID) will be assigned to each patient screened for the study. PIDs will include a site code and three-digit extension. PIDs should not be reassigned even if the patient fails to enter the study. The PID must be included on every CRF and patient blood sample. Each site must maintain a master list of PIDs in a central location. The patient registration and inclusion/exclusion must be entered on-line at www.cfar.ucsd.edu/intranet

Screening Site Clinical Labs

If plasma HIV-1 RNA and CD4+ T-cell counts were obtained at a CLIA-approved lab no more than 30 days prior to screening and results are available then these labs do not need to be repeated. Otherwise, a plasma HIV-1 RNA level and a CD4 cell count measurement need to be done at screening. Please record actual dates laboratories were done in the CRF.

All other study screening laboratories must be determined within 30 days of study entry (Day 0). Screening and entry evaluations must be separated by at least 48 hours. Hematology, chemistry and pregnancy testing will be coordinated through the site's local laboratory and results will be tracked by the CCTG Data Center.

Once the screening laboratories have been done the patient will be evaluated for study eligibility if all other entry criteria are satisfied.

The total blood volume for screening labs is 20 mL.

If the HIV RNA or other laboratory values are outside the eligible range, the site may re-screen a patient on one occasion. However, the study will not pay for additional re-screening laboratories.

Pre-Entry

Specimens for extended flow cytometry and PBMC storage need to be shipped by each site in real-time to the central laboratory (UCSD).

The total blood volume for pre-entry labs is 20 mL.

Entry

The entry evaluation should be scheduled within 30 days of the screening visit. Plasma and serum for storage should be obtained, however, specimens will be stored then shipped in batch on week 36 (end of study) along with other plasma, PBMC and serum specimens. The first dose of study medication should be given and witnessed by the study coordinator **after** drawing the entry laboratories.

The total blood volume for entry labs is 73 mL.

Lumbar puncture – 25 mL cerebral spinal fluid

6.2.2 On-Study Evaluations

Evaluations during the MVC treatment intensification period will occur on weeks 2, 4, 8, 12, and 24. An addition visit will occur after MVC treatment intensification on week 36. Study visits at week 2 and 4 will have a visit window period of 1 week. For study visits at week 8, 12, 24 and 36 there will be a 2 week visit window period. In instances of virologic failure and/or premature treatment discontinuation evaluations would also need to occur as soon as possible.

Total blood volume for laboratory evaluations during MVC treatment intensification (week 2 to week 24) will be approximately 200 mL.

Lumbar puncture – 25 mL cerebral spinal fluid (week 4 and 24)

Total blood volume for laboratory evaluations during post-MVC treatment intensification (week 36) will be approximately 40 mL.

6.2.3 Evaluations and plan for registered subjects that do not complete week 4 of the study:

- a. Those subjects that do not start treatment will be replaced and will have no follow-up evaluations performed.
- b. Subjects that discontinue antiretroviral therapy and/or MVC before week 4 will be replaced and will have no follow-up evaluations performed.

6.2.4 Evaluations and plan for randomized or registered subjects that complete week 4 but not the remainder of the study:

- a. Subjects who complete week 4 of the study but then discontinue their antiretroviral regimen and/or MVC will not be replaced and will not be discontinued from the study.

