6.3.6 Clinical Assessments

Complete Physical Exam

A complete physical examination will be performed at entry. Documentation must include a complete review of systems and any HIV-related, toxicity-related, or AIDS-defining events.

Targeted Physical Exam

A targeted physical examination will be based on any signs or symptoms previously identified that the subject has experienced within 30 days of entry or since the last visit. This examination will be performed at entry, weeks 12, 24 and 36 and in instances of virologic failure or premature treatment discontinuation if they should occur. Documentation must include any HIV-related, toxicity-related, or AIDS-defining events.

Height and Weight

Height and weight should be measured at study entry.

Signs and Symptoms

All signs, symptoms, deaths, and toxicities must be documented in the subject's record. At entry, record all signs/symptoms experienced within 30 days of entry on the CRFs. For all other visits including the time of confirmation of virologic failure, record all Grade ≥ 2 signs and symptoms, HIV-related and AIDS-defining events and deaths on the CRFs that have occurred since the last visit. Any signs or symptoms that lead to a change in treatment, regardless of Grade, must be recorded on the CRF. The source document must include date of onset and date of resolution, but the CRF will only record prevalence of a given adverse event since the previous study visit.

Refer to the Division of AIDS Table for Grading Adult Adverse Experiences, which can be found on the CCTG website: www.cctg.ucsd.edu

Diagnoses

The following should be recorded on the CRFs: HIV-related diagnoses, HIV-related malignancies, non-HIV related malignancies, myocardial infarctions,

hepatic failures, AIDS-defining events and death. Any other diagnosis that is, in the opinion of the site investigator, associated with study medications, should be recorded on the adverse event CRF. The source document must include date of diagnosis and date of resolution.

Karnofsky Performance Status

A Karnofsky performance status must be completed within 30 days before study entry.

Vital Signs

Temperature, pulse, and blood pressure collected at all visits and kept as a part of the source document.

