6.3.9 Virologic Studies

Plasma HIV-1 RNA

A screening HIV-1 RNA must be performed at the site's local laboratory within 30 days prior to study entry unless a HIV-1 RNA value is available from a CLIA-certified laboratory within 30 days of screening.

Plasma HIV-1 RNA should be performed at the same local laboratory during the study and collected at entry, weeks 4, 24, 36 and in instances of virologic failure.

Genotype Resistance and Tropism Assay

Samples for genotypic and viral tropic analysis obtained at the time of virologic failure will be tested in real time for subject management by the site's local laboratory. All resistance testing results should be scanned and uploaded on the on-line data collection system for review by the protocol team (www.cfar.ucsd.edu/intranet). The study does not provide resistance testing.

Stored Plasma

Stored Plasma will be collected at pre-entry, study entry, and weeks 4, 24 and 36.

* Specimens will be stored at the site's local laboratory and batched shipped to the central laboratory (UCSD) after completion of the study.

Blood volume for combined HIV RNA and stored plasma: 15 mL

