6.3.15 Adherence Assessment

Adherence assessment will be performed by the study coordinator using standard ACTG adherence format on weeks 2, 4, 8, 12, 24, and 36 of therapy and in instances of virologic failure and/or premature treatment discontinuation.

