8.2 Criteria for Discontinuation from the Study

- Failure to complete week 4 whether due to toxicity, poor adherence or need to stop drug.
- Request by the subject to withdraw.
- Request of the primary care provider if s/he thinks the study is no longer in the best interest of the subject.
- Clinical reasons believed life threatening by the physician, even if not addressed in the toxicity management of the protocol.
- Subject judged by the investigator to be at significant risk of failing to comply with the provisions of the protocol as to cause harm to self or seriously interfere with the validity of the study results.

- At the discretion of the CCTG, FDA, investigator, or pharmaceutical sponsors.

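### No follow-up for treated subjects who stop before week 4 (6.2.3b) conflicts with the stopping evaluation in 6.1 and 6.2.2 if read literally, and with toxicity follow-up in 7.1.2 and 7.2.3 on any reading

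*Combined protocol and SAP*

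**What the plan says.** Section 6.2.3 has two clauses. Clause a covers registered subjects who never start treatment: they are replaced and not evaluated further. Clause b covers those who start and then stop: "Subjects that discontinue antiretroviral therapy and/or MVC before week 4 will be replaced and will have no follow-up evaluations performed". Section 8.2 shows that toxicity stops fall in this group, because it discontinues a subject from the study for "Failure to complete week 4 whether due to toxicity, poor adherence or need to stop drug". By contrast, 6.2.4a says that subjects who stop after completing week 4 "will not be replaced and will not be discontinued from the study".

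Elsewhere the protocol asks for an evaluation when treatment stops early, with no week-4 limit:

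- 6.2.2: "In instances of virologic failure and/or premature treatment discontinuation evaluations would also need to occur as soon as possible".
- 6.1 has a column headed "Treatment Failure, Tox or Premature D/C". It is marked for adverse-event assessment, complete physical exam, hematology, chemistry/LFT, CD4/CD8 and HIV RNA, among others.
- 6.3.6 sets a targeted exam "in instances of virologic failure or premature treatment discontinuation if they should occur", and 6.3.15 sets the adherence assessment at weeks 2 to "36 of therapy and in instances of virologic failure and/or premature treatment discontinuation".

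Section 7 adds follow-up for particular events. Under 7.1.2, a symptomatic Grade 3 reaction attributed to maraviroc (MVC) stops the drug, and the subject is seen weekly until it resolves and only then leaves the study. Under 7.2.3 the same applies to a Grade 4 event that permanently stops MVC. Section 6.4 keeps safety monitoring and SAE reporting in force after treatment ends, whether or not follow-up visits are scheduled.

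**The concern.** A site with a subject who stops in week 3 finds one instruction to evaluate promptly and another to do no follow-up evaluation. The text does not say which prevails. The choice matters because chemistry/LFT and HIV RNA are not drawn at week 2; their first scheduled post-dose draw is at week 4. A site that follows 6.2.3b to the letter would skip the only other scheduled opportunity for either test. That includes the subject who has stopped background antiretroviral therapy as well as MVC, and the subject with a serious drug reaction still under way.

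Section 2.1.1.1 lists hepatotoxicity among the labelled warnings for MVC, and safety and tolerability are objective 1.2.4. The first weeks of dosing are therefore a poor place for conflicting safety instructions.

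**Working it through.** **Step 1. Who is covered.** Because 6.2.3a takes the never-treated, 6.2.3b concerns people with at least some exposure. Section 8.2 confirms that toxicity is among the reasons.

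**Step 2. What is scheduled (6.1).** The first dose follows the entry draw (6.2.1), so entry values are pre-dose.

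| Test | Before dosing | Week 2 | Week 4 | Discontinuation column |
|---|---|---|---|---|
| Chemistry/LFT | Screening | no | yes | yes |
| HIV RNA | Screening, entry | no | yes | yes |
| Hematology | Screening, entry | yes | yes | yes |
| CD4/CD8 | Screening, entry | yes | yes | yes |

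Scheduled post-dose draws for a subject who stops before week 4:

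| Test | 6.2.3b read literally | 6.1 column applied |
|---|---|---|
| Chemistry/LFT | 0 | 1 |
| HIV RNA | 0 | 1 |
| Hematology, CD4/CD8 | at most 1 | at most 2 |

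A week 4 visit held early, within its 1-week window, would supply both missing tests, but that subject has arguably completed week 4.

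**Step 3. The rules set against each other.**

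- *6.2.3b against 6.2.2 and 6.1.* These conflict if the stopping evaluation counts as a follow-up evaluation. Sections 6.3.6 and 6.3.15 describe parts of that same evaluation, so this is one conflict stated in several places.
- *6.2.3b against 7.1.2 and 7.2.3.* Weekly visits after the drug is stopped are follow-up on any meaning of the word. This conflict remains however the stopping visit is classified.
- *Weaker tension.* Section 7.2.4 removes a subject with Grade 3/4 rash only once it has settled to Grade 1 or less, which implies follow-up. Section 7.2.9 asks for follow-up after a creatinine stop, but only as medically indicated, so it fixes no visit.
- *No conflict.* Section 7.1.1 simply removes subjects who stop for a Grade 1 or 2 event.

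**Step 4. How many subjects.** The protocol gives no expected number of early stops. As an assumption, take r = 4.9%, the adverse-event stop rate quoted in 2.1.1.1 for twice-daily MVC, and apply it to n = 30 at constant hazard over T weeks. That section describes 48 weeks of treatment, while the title of the report it cites refers to 24-week results, so both are shown.

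p = 1 − (1 − r)^(4/T); expected = 30p; P(at least one) = 1 − (1 − p)^30

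- T = 24: p = 1 − 0.951^(1/6) = 0.00834; expected 0.25; P(at least one) = 22%.
- T = 48: p = 1 − 0.951^(1/12) = 0.00418; expected 0.13; P(at least one) = 12%.

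These count every early adverse-event stop. Some of those subjects will already have had an unscheduled test, so the figures overstate the adverse-event stops that would miss the draws. Stops for other reasons would add to the total.

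**The case against.** The best defence is that the natural reading removes most of the problem. The discontinuation evaluation sits under the on-study heading in 6.2.2 and has its own column in 6.1. It is a stopping visit, so the bar on follow-up evaluations could mean only the visits after it. Section 6.2.6 points the same way: it discontinues subjects who change background regimen before week 4, yet provides a toxicity visit for changes due to toxicity. One can add that a specific toxicity rule would ordinarily override a general replacement rule, and that 6.4 covers exactly the case where no follow-up is scheduled.

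Much of this stands. The milder reading is plausible, and safety oversight does not lapse. But no sentence states that reading or any order of precedence, 6.2.3a uses the same words for people who were never dosed, and 6.4 names no draw. The milder reading also leaves 7.1.2 and 7.2.3 contradicted.

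Three further inferences are tempting and should not be drawn:

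- *Section 7.2.8 also conflicts.* It holds MVC for Grade 4 AST/ALT until recovery and expects it to be resumed. That is a temporary hold, not the discontinuation that 6.2.3b covers.
- *The rule makes the last liver test stale.* Screening may be 30 days before entry, so the last scheduled LFT can be 30 + 28 = 58 days old at week 4. That is true of every subject in the trial and comes from the schedule.
- *HIV RNA is less well supported than chemistry.* Section 6.3.9 lists HIV RNA as "collected at entry, weeks 4, 24, 36 and in instances of virologic failure" and omits premature discontinuation, but 6.3.7 gives no visit list for chemistry/LFT either. Both draws rest on the 6.1 column.

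**Conclusion.** The point holds as a minor safety inconsistency. Section 6.2.3b contradicts 7.1.2 and 7.2.3 on any reading, and contradicts the stopping evaluation in 6.2.2 and 6.1 if taken literally. Under the literal reading, the loss is one scheduled post-dose chemistry/LFT and one scheduled post-dose HIV RNA per affected subject.

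The number affected is probably small: 0.13 to 0.25 expected adverse-event stops among 30. This assumes that a rate from viremic, triple-class-resistant patients carries over to suppressed ones and that the hazard is constant; the documents support neither assumption. The gap falls mainly on subjects who stop for reasons other than a laboratory abnormality, since those stopped for an abnormal result have already been tested.

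A reader might infer that early stoppers are left without safety oversight, or that the trial's main result is at risk. The documents support neither. Section 6.4 and the event-driven rules of section 7 still apply, and the missing draws do not enter the gene-expression comparison. The visit that is needed is already in the design; the wording of 6.2.3b puts it in doubt.

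**What to change.** Keep replacement for the microarray set. Limit the no-evaluation rule to 6.2.3a, where no dose was taken. Reword 6.2.3b so that any subject who took at least one dose, whatever the reason for stopping:

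1. has the evaluation in the 6.1 column "Treatment Failure, Tox or Premature D/C" as soon as possible;
2. has any follow-up that section 7 and 6.4 require; and
3. then has no further scheduled visits.

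Do not borrow the wording of 6.2.6b. It covers toxicity only and cites a visit name that is not a column in 6.1. Resistance and tropism testing, also marked in that column, should stay tied to confirmed virologic failure as in 6.2.7.

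The cost is a short protocol amendment and at most one added visit per affected subject, already described in 6.1. Blood volume is at most 3 (hematology) + 7 (chemistry/LFT) + 5 (CD4/CD8) + 15 (HIV RNA with stored plasma) = 30 mL. On the assumption above, that is 0.13 to 0.25 visits in all for adverse-event stops, plus one for each stop for another reason. Weekly toxicity follow-up adds nothing new, because 7.1.2 and 7.2.3 already require it.
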